## 5. TREATMENT OF SUBJECTS

### 5.1 Investigational product/treatment

See chapter 7.

### 5.2 Use of co-intervention (if applicable)

When patients use antibiotic drugs, probiotics (i.e. Yakult, Vifit, Activia etc), specific prebiotic supplements or specific vitamin supplements during the 3 weeks prior to the start of the riboflavin intervention they cannot participate in the study (see exclusion criteria). In addition participants are asked to refrain from specific supplements during the study period (see 'proefpersoneninformatie', attachment 8). In addition, participants are asked to refrain from alcohol, two days before test days. Participants are asked to refrain from smoking during the study period. Also participants are asked to refrain from intensive physical activity on the day before a test days.

### 5.3 Escape medication (if applicable)

Not applicable.

## 6. INVESTIGATIONAL PRODUCT

### 6.1 Name and description of investigational product(s)

Not applicable.

### 6.2 Summary of findings from non-clinical studies

Not applicable.

### 6.3 Summary of findings from clinical studies

Not applicable.

### 6.4 Summary of known and potential risks and benefits

Not applicable.

The effect of riboflavin supplementation on *Faecalibacterium prausnitzii* in Crohn's disease

### **6.5 Description and justification of route of administration and dosage**

Not applicable.

### **6.6 Dosages, dosage modifications and method of administration**

Not applicable.

### **6.7 Preparation and labelling of Investigational Medicinal Product**

Not applicable.

### **6.8 Drug accountability**

Not applicable.

## **7. NON-INVESTIGATIONAL PRODUCT**

### **7.1 Name and description of non-investigational product(s)**

#### Riboflavin

The non-investigational product used in this study is vitamin B2 (riboflavin) produced by DSM Nutritional Products. The riboflavin product (hard gel capsules) will be consumed orally. The daily dose will be ingested by taking one capsule per day at breakfast. Riboflavin is readily absorbed in the gastro-intestinal tract. Absorption is increased by intake of food.

#### Chroom-EDTA

Chroom-EDTA oral solution (see IMPD, versie 2, 23 Dec 2015) is a permeability marker which is often used in studies with human subjects. Chroom-EDTA is an extremely stable and inert complex with very limited toxicity.

### **7.2 Summary of findings from non-clinical studies**

Not applicable.

### **7.3 Summary of findings from clinical studies**

Not applicable.

#### Riboflavin

RISE-UP Study – UMCG  
March 2016 – Version 4

### **The effect of riboflavin supplementation on *Faecalibacterium prausnitzii* in Crohn's disease**

In a pilot-intervention study in healthy volunteers, it is shown that a riboflavin supplement increases the number of *F. prausnitzii*, and there appeared to be a positive effect on the production of butyrate (results not published yet).

#### Chroom-EDTA

The Chroom-EDTA test is used in this hospital before in the (by the ethical committee approved) COLIPI clinical trial ('*Identification of predictive parameters for colitis in melanoma patients treated with ipilimumab*' (METc 2012/085)).

## **7.4 Summary of known and potential risks and benefits**

#### Riboflavin

No adverse effects associated with riboflavin consumption from food or supplements have been reported. In a study by Schoenen and coworkers (1994) no short-term side effects were reported in 49 patients treated with 400 mg/day of riboflavin taken with meals for at least 3 months. The lack of harm resulting from high oral doses of riboflavin may be due to its limited solubility and limited capacity for absorption in the human gastrointestinal tract (Levy and Jusko, 1966; Stripp, 1965; Zempleni et al., 1996) and its rapid excretion in the urine (McCormick, 1994). Zempleni et al. (1996) showed that the maximal amount of riboflavin that was absorbed from a single oral dose was 27 mg. Similarly in a study by Stripp (1965) there was limited absorption of 50 to 500 mg of riboflavin with no adverse effects.

Based on the studies above as well as the widespread market presence of 200 mg riboflavin supplements without reported adverse effects, the (US) Council for Responsible Nutrition (CRN) published an opinion in 2013, setting a tolerable upper intake level (UL) of 200 mg/d riboflavin

Furthermore, the above (section 7.3) described finding of an increase in the number of *F. prausnitzii* and butyrate after riboflavin intake in healthy volunteers is promising. A similar (or even larger increase) in the number of *F. prausnitzii* (and butyrate) in the bowel of Crohn's disease patients by means of a simple supplement may result in the improvement of health of Crohn's disease patients. No adverse effects are known of this supplement, however vitamin B2 can cause a temporary and harmless bright yellow discoloration of the urine.

#### Chroom-EDTA

Chroom-EDTA oral solution is a safe diagnostic to measure the integrity of the intestines. To achieve better results in the research concerning the integrity of the intestines it is important that there are proper diagnostics. To achieve this the development of new markers is necessary. Without these markers it is more complicated to measure the effect of a therapy on the recovery of the intestines. As opposed to the labelled 51-Chroom-EDTA, the Chroom-EDTA solution used in this study has no gamma-radiation. The risk for the humans is very low. No side effects of Chroom-EDTA have been reported.

**RISE-UP Study – UMCG**

**March 2016 – Version 4**

## 7.5 Description and justification of route of administration and dosage

### Riboflavin

Riboflavin will be taken orally (conform the intended use). The product used in this study contains 100 mg of riboflavin per capsule. Participants will take 1 capsule of riboflavin per day at breakfast. The total daily dose is 100 mg. This is a commonly used dose for riboflavin supplementation (sold over the counter, without prescription). Participants will be advised to store the riboflavin product at room temperature in a dry place and to keep the product out of reach of children and pets.

### Chroom-EDTA

Patients will consume the Chroom-EDTA after a night of fasting (last meal 10 p.m. one day prior to the clinical visit). After emptying the bladder, subjects will consume a Chroom-EDTA drink, followed by a glass (240 ml) of water. The first dose (at baseline) will be given under supervision of the study nurse/investigator. After an additional two hours of fasting, participants are allowed to eat and drink again without restrictions. From consuming of the Chroom-EDTA-drink onwards for 24 hours, participants will collect urine. Urine samples will be collected in plastic bottles containing 10 ml 6 mol/l hydrochloric acid to prevent bacterial deterioration.

## 7.6 Dosages, dosage modifications and method of administration

### Riboflavin

No method of administration modifications will take place in the present study.

### Chroom-EDTA

Chroom-EDTA solution is prepared (20 µmol/ml), using the method of Binnerts et al, in a food-grade environment and complete formation and stability is checked. Drinks will be filled with exact amounts of Chroom-EDTA, resulting in drinks containing 400 µmol Chroom-EDTA. The drinks will be produced in the pharmacy of A15 in accordance with GMP license (see attachment).

## 7.7 Preparation and labelling of Non Investigational Medicinal Product

Prior to the start of the study, DSM Nutritional Products will provide riboflavin and be responsible for packaging and labelling of the study supplement. The supplement will be packed into bottles of 23 capsules (21 days supplementation of 1 capsule per day + 2 spare capsules). The packages will be labelled in accordance with applicable laws and regulations. Labels on the study products will contain information required for usage and identification

## The effect of riboflavin supplementation on *Faecalibacterium prausnitzii* in Crohn's disease

purposes. The investigator will store the study product in a secure, limited access storage area at a cool dry place (between 15°C and 25°C), and protected from extremes of light and humidity.

### 7.8 Drug accountability

#### Riboflavin

Participants will receive a bottle of 23 capsules at the start of the study. When possible products of the same batch will be used in all subjects. Subjects should return all unused capsules to the investigator. The investigator will then throw away the capsules.

#### Chroom-EDTA

The Chroom-EDTA oral solution will be labelled by the pharmacy A15. Chroom-EDTA will be stored at the pharmacy of the UMCG (contact person [name], [name], [name] and [name]). On the day of administration the investigator will collect the Chroom-EDTA at the pharmacy.

## 8. METHODS

### 8.1 Study parameters/endpoints

#### 8.1.1 Main study parameter/endpoint

The main study parameter is the number of *F. prausnitzii* bacteria per gram of faeces. This will be measured with FISH and specific probes for *F. prausnitzii* and all bacteria will be counted. (28) This will be determined in the faeces samples at different time points. The number of bacteria from before and after the riboflavin intervention will be compared.

#### 8.1.2 Secondary study parameters/endpoints

- Before and after the riboflavin intervention, faeces samples will be analyzed for:
  - The number of butyrate producing bacteria other than *F. prausnitzii* per gram faeces, in particular Roseburia species, as measured by FISH. The numbers before and after the intervention will be compared.
  - The number of Enterobacteriaceae, including *E. coli* per gram of faeces. The numbers before and after the intervention will be compared.
  - The ratio of Enterobacteriaceae / *Faecalibacterium* is a measure of the improvement in the dysbiosis in intestinal microbiota.
  - The concentration of fatty acids in the stool (i.e. butyrate).
  - The level of faecal calprotectin will be measured at different time points, as marker of activity of Crohn's disease.
- Faeces pH.

### The effect of riboflavin supplementation on *Faecalibacterium prausnitzii* in Crohn's disease

- Microbiota analysis by pyrosequencing.
- The Harvey Bradshaw Index, a measure of disease severity, will be taken before and after the intervention (see paragraph 3 and attachment 1).
- The validated IBD-Q questionnaire will be taken before and after the intervention (see document F1: IBD-Q).
- Blood and a urine sample (see paragraph 3, study design) will be taken before and after the intervention.
- A Chroom-EDTA test will be performed at two time points.
- Biomarkers of gut permeability will be measured before and after the intervention.
- Electrical current measurements of faeces and cell culturing experiments.
- Adverse events (AE's), serious adverse events (SAE's) and suspected unexpected serious adverse reactions (SUSAR's).

#### 8.1.3 Other study parameters

Not applicable.

## 8.2 Randomisation, blinding and treatment allocation

In this current study participants will not be randomized. Also no blinding will take place. The study is designed in such a way that participants are their own controls.

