## The effect of riboflavin supplementation on *Faecalibacterium prausnitzii* in Crohn's disease

analysis of the electrical current and culturing experiments. The concentration of certain fatty acids in the stool will be measured. In this butyrate is of particular interest. In addition, a portion of the faeces sample will be stored, for microbiome analysis. Microbiota will be analysed with pyrosequencing. All findings in the area of intestinal wellbeing, frequency of defecation, and the consistency of the faeces will be recorded in a questionnaire on two time points (IBD-Q, see F1, 'vragenlijst IBD-Q'). Also faeces will be collected for analysis of the faecal calprotectin. Faecal calprotectin is a neutrophilic protein in faeces, and considered to be a useful non-invasive tool, for differentiating IBD from non-organic disease. Also it is shown that repeated measurements of faecal calprotectin can predict disease course. (25) This measurement will be performed twice: at baseline and on the last day of the riboflavin intervention. For the complete schedule of activities and the different time points see Table 1 and the checklist of the participants. On two timepoints (day 17 and day 42) all samples will be collected (either with car) or participants will bring the samples to the hospital themselves.

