### 4.4 Sample size calculation

The primary objective in this study is to investigate whether the number of *F. prausnitzii* increases as result of a riboflavin intervention in patients with Crohn's disease. A power calculation has been performed ([name]). First the mean increase in *F. prausnitzii* as seen in the healthy volunteer riboflavin pilot study was calculated. In this study bacteria were measured per grams of faeces. The amount of bacteria were measured with FISH. The mean increase was  $6.14 \cdot 10^8$  bacteria per gram of faeces per volunteer (SD:  $1.56 \cdot 10^9$ ). In an article of Swidsinski et al 2008 the number of *F. prausnitzii* bacteria in the bowel was measured in 82 Crohn's disease patients using FISH. (27) The mean of *F. prausnitzii* was  $5.6 \cdot 10^9$  bacteria / ml of faeces (SD:  $5.9 \cdot 10^9$ ). In this same article, it is shown that the mean of *F. prausnitzii* in healthy volunteers (n=32) is much higher:  $14.9 \cdot 10^9$  bacteria / ml faeces (SD:  $4.5 \cdot 10^9$ ). In the article of Swidsinski, the number of *F. prausnitzii* is roughly 2.5 times higher in the healthy group as opposed to the group with Crohn's disease. We expect that the same ratio of *F. prausnitzii* between healthy volunteers and Crohn's disease patients will be the case in our population. A similar increase as seen in the healthy volunteer group is hypothesized to take place after the riboflavin intervention. This results in an expected mean increase of *F. prausnitzii* of  $2.45 \cdot 10^8$  bacteria / grams of faeces in our Crohn's disease group (SD:  $6.22 \cdot 10^8$ ). With a one sided test, with a power of 0.80 and an alpha of 0.05, this will result in a sample size of 42 patients for the group in remission. Since we want to study the effect in two experimental groups (one group in remission, and one group with active disease), 84 patients will be recruited.

In this study an adaptive design will be used. When the first 12 patients in the disease in remission group are included and have completed the study procedures, the collected faeces samples will be analyzed. The number of *F. prausnitzii* with FISH will be determined and compared on different timepoints (primary endpoint). Also the ratio of enterobacteriaceae / *F. prausnitzii* will be determined. When the increase of the *F. prausnitzii* bacteria is less than

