## 8.3 Study procedures

Standard faeces samples (five time points: day 0, day 6, day 17, day 28 and day 42) will be divided into three fractions:

- The first fraction (0.5 gram) will be fixed with 4% paraformaldehyde in Phosphate Buffered Saline (PBS) and used for FISH analysis with specific probes. (29)
- The second fraction (100 µgram) will be used for the analysis of volatile fatty acids.
- The third fraction (0.5 gram) will be stored for microbiome analysis by Next Generation Sequencing (microbiome analysis, by 16S RNA sequencing and MiSeq Illumina).
- The remainder is retained for dry weight determination, pH analysis and lactate analysis.

Faeces samples on glycerol, cysteine and PBS mix (two time points: day 6 en day 28):

-These samples will be used for the electrical current measurements of faeces and cell culturing experiments.

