#### FISH analysis

Fluorescent probes for *F. prausnitzii* (*F. prau*), Clostridium group XIVa (*Erec*), *Roseburia* (*rint*), *Enterobacteriaceae* (EC1535) and total bacteria (EUB338) will be used to measure the effect of the riboflavin intervention. The hybridized bacteria will be counted with an epifluorescence microscope DMRA2 of Leica, automatic system, with a user modified version of Leica Q-win software (Leica, Wetzlar, Germany). (30)

RISE-UP Study – UMCG

March 2016 – Version 4

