## 10. STATISTICAL ANALYSIS

The study population consists of two groups (an active disease group and a disease in remission group). The primary endpoint is number of *F. prausnitzii* bacteria per grams of faeces. The two groups will first be statistically analysed separately. A non-parametric statistical test will be used in which the number of *F. prausnitzii* bacteria prior to the intake of riboflavin (control period) will be compared with the number of bacteria after intake of riboflavin (i.e. day 28). This will be analyzed with the paired Wilcoxon test. For analysis between groups (active disease and disease in remission) the Mann-Whitney U test will be used. The MiSeq Illumina data will be analyzed with a multi-parametric test.

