## 12. ADMINISTRATIVE ASPECTS, MONITORING AND PUBLICATION

### 12.1 Handling and storage of data and documents

The handling of personal data complies with the Dutch 'Personal Data Protection Act' (Dutch: 'wet bescherming persoonsgegevens (wbp)'). All related documents and records will be kept and archived for at least 15 years. Data of participants will be handled confidentially and a coded identification number will be used to link the data to the specific patient. This specific data that can be linked to a patient will be stored separately. The coded identification number used in this study respectively consists of: the acronym: RISE-UP combined with the date and number of inclusion. For example the first participant included of the first of June 2014 would have the code identification number: RISE-UP/01-06-2014/01. The principal investigator will safeguard the key to the code.

The case record forms (CRF's) will be completed and signed for correctness by the investigators. By signing this CRF, the medical investigator is responsible for the legibility, completeness and correctness of the CRF.

Changes, errors and/or additions to the original CRFs shall be corrected by drawing a single line through the incorrect entry and writing as close to the original as possible. The correction must be initialled and dated by the authorized person making the changes. If necessary the reason for the changes must be given.

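### The plan does not mask the FISH count to sampling day or keep a patient's samples in one run, so a consistent before-after count shift is not excluded

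*Combined protocol and SAP*

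**What the plan says.** Section 8.2 says that participants are not randomised and serve as their own controls, and adds "Also no blinding will take place". It makes no separate statement about laboratory staff.

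Section 8.3 lists the stool time points: "Standard faeces samples (five time points: day 0, day 6, day 17, day 28 and day 42) will be divided into three fractions". Its FISH paragraph names the probes and describes the microscope as an "automatic system, with a user modified version of Leica Q-win software". It does not cover masking of sampling day, allocation of samples to runs, counting order or run controls.

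Section 3 (riboflavin intervention) says "On two timepoints (day 17 and day 42) all samples will be collected". By date, the stools of days 0, 6 and 17 belong to the first collection and those of days 28 and 42 to the second.

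Section 10 compares the control-period count with the count after riboflavin, naming day 28, by a paired Wilcoxon test within each disease group.

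The only statement on when FISH is run is in Section 4.4. Once the first 12 remission patients "are included and have completed the study procedures, the collected faeces samples will be analyzed". Nothing is said for the other 84 − 12 = 72 patients.

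Section 12.1 says that "a coded identification number will be used to link the data to the specific patient". That concerns confidentiality of data; tube labels are not described.

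**The concern.** In a single-arm before-after design, the primary test attributes any systematic difference between before and after samples to the supplement. No untreated group would show the same shift and cancel it. Fixing, dilution, hybridisation and the settings of the counting software can each move a count, and knowledge of the sampling day can influence handling.

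Here the samples being contrasted reach the hospital at different times, and no written rule brings them together in the assay or hides which is which. The day may also be easy to recognise. The subject code contains the inclusion date (Section 12.1), so a dated tube would give the study day away. Only days 6 and 28, one control day and the primary endpoint day, have the extra glycerol container (Sections 3 and 8.3).

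The planned effect is small relative to the level of the count, so even a modest shift would matter for the primary endpoint.

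**Working it through.** **Inputs, all from Section 4.4:** expected rise 2.45e8 per gram; SD of change 6.22e8; one-sided alpha 0.05; power 0.80; n = 42 per group; cited Crohn's mean 5.6e9 per ml; pilot SD of change 1.56e9. One assumption is added: 1 ml is taken as 1 g. The size of any shift is also an assumption, because the documents give none.

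**Step 1. Reproduce the plan's figure.** Effect size = 2.45e8 / 6.22e8 = 0.394. For a one-sided paired t-test (noncentral t), power is 0.798 at n = 41 and 0.807 at n = 42. The stated 42 reproduces, so the sample size arithmetic is not in question.

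**Step 2. Put the effect on the scale of the count.** 2.45e8 / 5.6e9 = 0.04375, about 4.4%.

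**Step 3. Rejection rate with no riboflavin effect and a constant upward shift.** Let the shift be p × 5.6e9 in every patient. The noncentrality is (p × 5.6e9 / SD) × √42, with √42 = 6.48. With SD 6.22e8:

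| Shift p | Shift in count | Shift / SD | Noncentrality | One-sided t | Simulated Wilcoxon |
|---|---|---|---|---|---|
| 0% | 0 | 0 | 0 | 5% | about 5% |
| 1% | 5.6e7 | 0.090 | 0.58 | 14% | 14% |
| 2% | 1.12e8 | 0.180 | 1.17 | 31% | 30% |
| 3% | 1.68e8 | 0.270 | 1.75 | 53% | 52% |
| 4.4% | 2.45e8 | 0.394 | 2.55 | 81% | 79% |

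The simulations used normal changes and 20,000 runs per row. At 4.4% the shift equals the whole planned effect, so the rejection rate equals the planned power.

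**Step 4. Downward shift.** With the planned rise truly present, a consistent downward shift of 1% or 2% lowers power from 81% to 61% or 39% (t-test).

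**Step 5. What the figures depend on.**

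- *Direction.* If the shift has random sign from patient to patient (1% to 4.4%), the simulated false-positive rate stays at about 5%.
- *SD.* With the pilot's unscaled SD of 1.56e9, a consistent 2% shift gives 1.12e8 / 1.56e9 = 0.072. The noncentrality is 0.47 and the false-positive rate about 12%.

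**Step 6. Contrasts within a collection.** Day 17 (on riboflavin) against days 0 and 6 lies within the first collection; day 28 (on) against day 42 (off) lies within the second. A shift tied to collection would move days 28 and 42 together and leave day 17 against days 0 and 6 untouched. The primary test uses neither contrast. Both also mix times from sampling to collection: 17 and 11 days for days 0 and 6 against 0 for day 17, and 14 days for day 28 against 0 for day 42. Carry-over at day 42 is possible. They are partial checks only.

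**The case against.** A reader might infer that every control stool is counted in a different run from its own day-28 stool, so that drift and riboflavin effect cannot be separated at all. The documents do not support that. A collection date is not an assay run, and nothing says that samples are counted on arrival. For the first 12 remission patients, the samples are analysed after completion, when all five stools are in hand and could share a run. The within-collection contrasts give some separation. The total-bacteria probe, counted in the same assay, could reveal a general dilution or fixation shift.

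A reader might also infer that readers definitely count with knowledge of the day. Section 8.2 is a general statement in a section about participants, Section 12.1 does not describe tube labels, and automated counting limits reader bias.

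Finally, ordinary run-to-run variation need not push all patients the same way. If patients enter over time, one patient's early stools and another's late stools are handled in the same period. The error rates above need a shift of one sign, and nothing in the documents points to one.

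All of this stands, and it limits the claim. It does not close the gap: same-run counting is possible but nowhere required, the only statement on blinding is that there is none, and the primary test has no protection of its own. Automation does not cover sample preparation, and the software is described as modified by its user.

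**Conclusion.** The point holds as an unprotected risk to the primary endpoint. It is not a demonstrated bias. The plan neither masks FISH to sampling day nor requires one patient's samples to be counted together. A consistent directional shift is therefore not excluded, and the primary test would not separate it from the supplement effect.

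The false-positive rates of about 14%, 30% and 53% are sensitivity figures. They rest on a same-direction upward shift of 1%, 2% or 3% in all patients, SD 6.22e8, n = 42, and a per-ml mean applied to a per-gram endpoint. The finding gives no reason to call the trial invalid or to change its sample size. It is a safeguard that should be added, because patients in this design cannot be blinded to the supplement period but the laboratory can.

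**What to change.** In Sections 8.2 and 8.3:

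- State that patients and physicians are unblinded and that laboratory staff are blinded to sampling day.
- Label FISH aliquots with random sample numbers and withhold the link list from the laboratory until the counts are locked.
- Hybridise and count all five samples of a patient in one run, in random order, with a run control.
- Fix every stool at the same point after receipt, and record storage time.
- Apply the same to the fatty acid assay where feasible. Leave out the calprotectin result used to assign groups at entry, which is needed at once.

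The cost is a label list and a short procedure change, with no extra visits or patients. Counts wait until after day 42. The 12-patient look already waits for completed patients and is not delayed. Aliquots from the first collection are stored about 42 − 17 = 25 days longer than those from the second, and fixing may still differ by collection. The change therefore reduces handling differences between before and after samples without fully removing them, which is why storage time should be recorded.
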